#### 1.2.2.4.2 Open Label Period and Long-Term Extension

The following exploratory endpoints will be assessed at the end of the open label period (Week 53) and after 12 months on the LTE period.

- Proportion of participants who received placebo during the blinded part and able to achieve durable platelet response during the open label part. Durable platelet response is defined as platelet counts at or above 50,000/ $\mu\text{L}$  for  $\geq$  two-thirds of at least 10 non-missing weekly scheduled platelet measurements during the last 16 weeks of the 28 of the open label period in the absence of rescue therapy, provided that at least 3 non-missing weekly scheduled platelet measurements are at or above 50,000/ $\mu\text{L}$  during the last 8 weeks of the 28-week open label period
- Percentage of weeks with platelet count  $\geq 50,000/\mu\text{L}$  OR between  $\geq 30,000/\mu\text{L}$  and  $< 50,000/\mu\text{L}$  and at least doubled from baseline
- Proportion of participants with complete response (defined as platelet count  $\geq 100,000/\mu\text{L}$  on 2 consecutive visits at least 5 days apart and no bleeding or rescue ITP therapy use on and through these two visits)
- Proportion of participants who have a platelet count that exceeds 250,000/ $\mu\text{L}$  or 450,000/ $\mu\text{L}$  (for participants on TPO-RAs)
- Proportion of participants requiring rescue therapy
- Change from baseline on the Fatigue (Item 10 of the ITP-PAQ; physical fatigue), Psychological, Fear, Social Activity, Women's Reproductive Health and Work domains of the ITP-PAQ in adult participants ( $\geq 18$  years)
- Change from baseline in IBLIS assessment

- Change from baseline in QOL as measured by the EuroQOL-Dimensions-5 Level in adult participants ( $\geq 18$  years)
- Percent change from baseline on corticosteroids (CS) dose
- Percent change from baseline on TPO-RA dose
- Proportion of participants who switch to rilzabrutinib as a monotherapy during the first year of the LTE period
- Proportion of participants who decrease their CS dose  $>50\%$  relative to baseline values during the first year of the LTE
- Proportion of participants who manage to reduce their dose or stop TPO-RA agonists during the first year of the LTE

### 1.2.3 Estimands

Primary estimand defined for main endpoints are summarized in [Table 2](#) below. More details are provided in [Section 3](#).

For all estimands, the comparison of interest will be the comparison of SAR444671 rilzabrutinib 400 mg BID vs. placebo.

The population of interest is the ITT population of adult participants aged  $\geq 18$  and pediatric participants aged 10 to  $<18$  years (recruitment of pediatric participants aged 10 to  $<18$  from EU [EEA] countries only) with persistent or chronic immune thrombocytopenia. The primary analysis will be based on adult participants (see details in [Section 3.8](#)).

**Table 2 - Summary of primary estimand for main endpoints**

Endpoint Category (estimand)	Estimands			
	Endpoint a	Population	Intercurrent event(s) handling strategy	Population-level summary (Analysis and missing data handling)
Primary objective: To demonstrate the efficacy of rilzabrutinib versus placebo in participants with refractory/relapsed ITP, based on the durability of platelet response during the last 12 weeks of the 24-week blinded treatment period in the absence of rescue therapy				
Primary endpoint (Composite estimand)	
Durable platelet response is defined as the proportion of participants able to achieve platelet counts at or above 50,000/<math>\mu</math>L for <math>\geq</math>two-thirds of at least 8 non-missing weekly scheduled platelet measurements during the last 12 weeks of the 24-week blinded treatment period in the absence of rescue therapy, provided that at least 2 non-missing weekly scheduled platelet measurements are at or above 50,000/<math>\mu</math>L during the last 6 weeks of the 24-week blinded treatment period (Definition 1) b
 
Country-specific definition c : Durable platelet response is defined as the proportion of participants able to achieve platelet counts at or above 50,000/<math>\mu</math>L for at least 8 out of the last 12 weeks of the 24-week blinded treatment period in the absence of rescue therapy (Definition 2)
	ITT	
1) Rescue medication: participants will be considered as non-responders if taking rescue medication after 8 weeks of double-blind treatment and before Week 25 (or last IMP intake, whichever earlier) (composite strategy).
 
2) Discontinuation of study intervention before Week 25 due to lack of response or related adverse events per eCRF: participants will be considered as non-responders (composite strategy).
 
3) Discontinuation of study intervention before Week 25 due to reasons other than the aforementioned: data during the double-blind on-treatment period will be included in the analysis. Post-treatment data will be considered to have had no platelet response (composite strategy)
	
Adults: p-value from Cochran-Mantel-Haenszel (CMH) test adjusted by randomization stratification factors d. Mantel- Haenszel common risk difference and 95% CI based on Mantel-Haenszel stratum weights (1) and the Sato variance estimator (2). Pediatrics: Descriptive.
 
For Definition 2, Missing data due to Covid-19 (per eCRF) are assumed missing at random and will be imputed using the participant's median value of available (a minimum of 3 available required) weekly platelet counts during the last 12 weeks of double-blind on-treatment period. Otherwise, missing data will be considered as no response.

Endpoint Category (estimand)	Estimands			
	Endpoint a	Population	Intercurrent event(s) handling strategy	Population-level summary (Analysis and missing data handling)
Secondary objective: To evaluate the effect of rilzabrutinib versus placebo on the number of weeks with platelet response, the time to first platelet response, the proportion of participants requiring rescue therapy over the 24-week blinded treatment period, the change from baseline in physical fatigue (Item 10 of the ITP-PAQ) in adults at Week 13, and the change from baseline in IBLS assessment at Week 25				
Secondary endpoint (Hypothetical + composite estimand)	
# weeks with platelet count <math>\geq 50,000/\mu\text{L}</math> OR <math>30,000/\mu\text{L}</math> to <math>< 50,000/\mu\text{L}</math> and doubled from baseline in the absence of rescue therapy
 
# weeks with platelet count <math>\geq 30,000/\mu\text{L}</math> and doubled from baseline in the absence of rescue therapy
	ITT	
1) Rescue medication: platelet counts will be censored for 4 weeks after the use of rescue therapy. That is, the weeks from the date when the rescue medication is initiated up to 4 weeks after the use of rescue medication will be considered to have had no platelet response (hypothetical strategy).
 
2) Discontinuation of study intervention before Week 25: data during the double-blind on-treatment period will be included in the analysis. Post-treatment data will be considered to have had no platelet response (composite strategy).
	
Adults: p-value, least squares mean number of weeks of response and 95% CI from a mixed-effect model with repeated measures (MMRM) approach on the binary response data including treatment, randomization stratification factors d, week, treatment-by-week interaction as categorical fixed effects.
 
Pediatrics: Descriptive.
 
Missing data will be considered as no response. If no platelet measurement is available at a specific weekly visit, that week will be considered to have had no platelet response.

Secondary endpoint (Hypothetical + composite estimand)	Time to first platelet count of $\geq 50,000/\mu\text{L}$ OR $30,000/\mu\text{L}$ to $< 50,000/\mu\text{L}$ and doubled from baseline in the absence of rescue therapy	ITT	
1) Rescue medication: platelet counts will be censored for 4 weeks after the use of rescue therapy. That is, the weeks from the date when the rescue medication is initiated up to 4 weeks after the use of rescue medication will be considered to have had no platelet response (hypothetical strategy).
 
2) Discontinuation of study intervention before Week 25: data during the double-blind on-treatment period will be included in the analysis. Post-treatment data will be considered to have had no platelet response (composite strategy).
	
Adults: p-value from stratified log-rank test adjusted by randomization stratification factors d. Hazard ratio and 95% CI from Cox regression model with treatment group and randomization stratification factors d as covariates.
 
Pediatrics: Descriptive.
 
Missing data will be considered as no response. If no platelet measurement is available at the weekly visit, that week will be considered to have had no platelet response.
 
Participants who never responded will be censored at 1 week after Week 25 if prematurely discontinued due to related AE or lack of efficacy; Otherwise censored at the last platelet count assessment during the double-blind on-treatment period.

Endpoint Category (estimand)	Estimands			
	Endpoint a	Population	Intercurrent event(s) handling strategy	Population-level summary (Analysis and missing data handling)
Secondary endpoint (while on-treatment estimand)	% participants requiring rescue therapy	ITT	Rescue therapy after 1st double-blinded IMP administration and before Week 25 (or last double-blinded IMP administration, whichever earlier) will be included in the analysis (while on-treatment strategy).	Adults: p-value from stratified log-rank test adjusted by randomization stratification factors d . Hazard ratio and 95% CI from Cox regression model with treatment group and randomization stratification factors d as covariates. Estimated % participants rescued at Week 25 based on Kaplan-Meier method. Pediatrics: Descriptive.  Participants who have not been rescued any time during the 24-week double-blind treatment period will be censored at Week 25 (Day 169) visit (or last double-blinded IMP administration, whichever earlier).
Secondary endpoint (Composite + hypothetical estimand)	Change from baseline in physical fatigue (Item 10 of the ITP-PAQ) in adults at Week 13 b	ITT	1) Rescue therapy (after 8 weeks of double-blind treatment): data after the initiation of rescue therapy will be imputed by the participant's worst post-baseline value on or before the use of rescue therapy, ie, worst observation carried forward, (for participants whose post-baseline values are all missing, the baseline value will be used to impute the missing Week 13 value) (composite strategy). 2) Discontinuation of study intervention before Week 13 due to lack of response or related adverse events: the same handling as 1) above (composite strategy). 3) Discontinuation of study intervention before Week 13 due to reasons other than the aforementioned: data during the double-blind on-treatment period up to Week 13 will be included in the analysis. Post-treatment data will be considered missing (hypothetical strategy).	Adults only: p-value, least squares mean difference and 95% CI from an analysis of covariance (ANCOVA) model with treatment group, randomization stratification factors d and geographic region as fixed effects, and baseline value as a covariate.  Missing data handling: A multiple imputation approach assuming missing at random will be used to impute missing Week 13 value, using all data during the double-blind on-treatment period up to Week 13 from participants who did not take rescue medication (after 8 weeks of double-blind treatment), nor discontinued before Week 13 due to related AE or lack of response. Note: before imputation (worst observation carried forward or multiple imputation), data will be set to missing for 4 weeks after the use of rescue therapy.

Endpoint Category (estimand)	Estimands			
	Endpoint a	Population	Intercurrent event(s) handling strategy	Population-level summary (Analysis and missing data handling)
Secondary endpoint (Composite + hypothetical estimand)	Change from baseline in IBLS assessment at Week 25 c	ITT	The same handling as for ITP-PAQ Item 10 above except that Week 25 will replace Week 13.	Adult population: p-value from ANCOVA with treatment group and randomization stratification factors d and geographic region as fixed effects and baseline value as a covariate.  Pediatrics: Descriptive.  The same handling of missing data as for ITP-PAQ Item 10 above except that Week 25 will replace Week 13.

a Additional secondary/exploratory endpoints that are not included in this table will be handled with a similar strategy by the endpoint type (ie continuous, proportion, time-to-event) during respective periods (double-blind, open-label, long-term extension).

b Not applicable to countries within the EU (EEA countries) and UK.

c Applicable to countries within the EU (EEA countries) and UK only.

d Randomization stratification factors are splenectomy status (yes, no) and severity of thrombocytopenia (platelet counts <15,000/μL, ≥15,000/μL).

## 2 ANALYSIS POPULATIONS

The following populations for analyses are defined.

**Table 3 - Populations for analyses**

Population	Description
Screened	All participants who signed the informed consent form (ICF).
Randomized	All participants from screened population who have been allocated to a randomized intervention by IRT regardless of whether the intervention was received or not.
Intent-to-treat (ITT)	All randomized participants. Participants will be analyzed according to the intervention allocated by randomization.
Modified ITT (mITT)	All participants from ITT population who are exposed. Participants will be analyzed according to the intervention allocated by randomization.
Population without trial impact (disruption) due to COVID-19	All randomized participants without any major deviation related to Covid-19.
Safety	All randomized participants who take at least 1 dose of study intervention, regardless of the amount of treatment administrated. Participants will be analyzed according to the intervention they actually received (ie, "as-treated" defined below).
Pharmacokinetic (PK)	All randomized and exposed participants (safety population) with at least one post-baseline PK sample. Participants will be analyzed according to the intervention they actually received.
Open-Label (OL)	All participants who are exposed to active intervention (ie, rilzabrutinib) during the open-label period (ie, between the first OL visit at the nominal protocol visit Week 25 and the first LTE visit at the nominal protocol visit Week 53).
Long-term-extension (LTE)	All participants who are exposed to active intervention (ie, rilzabrutinib) during the LTE period (ie, on or after the first LTE visit at the nominal protocol visit Week 53).
Rilzabrutinib safety	All randomized participants who take at least 1 dose of the active intervention (ie, rilzabrutinib) during the study (ie, exposed to rilzabrutinib in the safety population during double-blind, open-label or LTE period).

Participants exposed to study intervention before or without being randomized will not be considered randomized and will not be included in any analysis population. The safety experience of these participants will be reported separately.

Randomized participants for whom it is unclear whether they took the study intervention will be considered as exposed and will be included in the safety population as randomized.

For any participant randomized more than once, only the data associated with the first randomization (except if the first randomization is done by error) will be used in any analysis population. The safety experience associated with any later randomization will be reported separately.

For participants receiving more than one study intervention during the study, the intervention group for as-treated analyses will be the intervention group as randomized if the participant received at least one administration as-randomized. The participants in the as-treated “placebo” group will not be included in the Rilzabrutinib safety population ([Table 3](#)) if they are not exposed to rilzabrutinib during the open-label or long-term extension treatment period.

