10.3. Analysis Populations

10.3.1. Safety Population

All participants who are randomized and receive at least one dose of study medication will be included in the Safety Population. The Safety Population is the primary analysis population for safety. Participants will be analyzed according to the treatment they actually received, not necessarily the treatment they were allocated to at randomization. Results for the blinded treatment period will be presented “as treated.” Further details will be provided in the SAP on how data collected during the open-label period will be analyzed.

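### The SAP text under Table 3 drops from the rilzabrutinib safety population a placebo participant who took rilzabrutinib by mistake in the double-blind period, although Table 3 includes that participant

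*SAP*

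**What the plan says.** The rilzabrutinib safety row of SAP Table 3 takes in "All randomized participants who take at least 1 dose of the active intervention (ie, rilzabrutinib) during the study", explained as those "exposed to rilzabrutinib in the safety population during double-blind, open-label or LTE period". Membership depends on doses taken, and the double-blind period is named.

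The text below the table deals with participants who received more than one intervention. For them, "the intervention group for as-treated analyses will be the intervention group as randomized if the participant received at least one administration as-randomized". The next sentence says that participants in the as-treated placebo "group will not be included in the Rilzabrutinib safety population" "if they are not exposed to rilzabrutinib during the open-label or long-term extension treatment period". The double-blind period is absent from that condition.

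Other places bear on the same population:

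- SAP 3.1 bases the cumulative safety analyses on it and starts its treatment-emergent period at the first administration of rilzabrutinib.
- Footnote f of SAP Table 7 and footnote c of SAP Table 9 start the cumulative data at the first rilzabrutinib dose, whichever period that falls in.
- SAP 3.6 reports separately the adverse events of participants who were not treated as randomized.
- Protocol 10.3.1 states the general principle for safety: "Participants will be analyzed according to the treatment they actually received, not necessarily the treatment they were allocated to at randomization".

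**The concern.** The population exists to gather everyone who was exposed to the drug. A rule that removes an exposed person because of a group label works against that purpose, and here it also contradicts the table it refers to. Two programmers working from the same section could build different populations and both claim to follow the SAP.

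What is at stake is the completeness of the cumulative outputs. A person who is not in the population is missing from numerators, denominators and participant-years alike. The situation can arise: under Protocol Section 4 a participant without a platelet response at Week 12 may leave the study instead of entering open label, so a placebo participant can finish without any open-label drug.

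**Working it through.** The plan gives no figure to reproduce. The check is to apply both rules to each exposure pattern that a placebo-randomized participant could have.

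| Pattern | As-treated group | Table 3 | Text below Table 3 |
|---|---|---|---|
| (a) Placebo only, no open label or LTE | Placebo | Out | Out |
| (b) Placebo plus rilzabrutinib by mistake in the double-blind period, no open label or LTE | Placebo | **In** | **Out** |
| (c) As (b), then open label or LTE | Placebo | In | In |
| (d) Rilzabrutinib only, by mistake | Rilzabrutinib | In | In |

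The rules differ only for (b). The exclusion sentence adds nothing for (a), whom Table 3 already leaves out, and does not reach (c) or (d). Its only practical effect is therefore in the one case where it contradicts the table. The design gives a placebo participant no planned route to rilzabrutinib while blinded, so (b) means a dispensing or dosing error.

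**Outputs affected.** These are the ones run on this population:

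- exposure (SAP 3.6.1);
- the cumulative column of Table 7, which covers all treatment-emergent events, serious events and deaths among others;
- the cumulative column of Table 9, which includes the plot of peak ALT against peak bilirubin and the return-to-baseline summary.

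**Illustrative size.** The number of participants in pattern (b) is not in the documents; I assume k = 1, 2 or 3 adults. Planned adult arms are 129 and 65 (SAP Section 4). Let N be the pool without the k people and x its number of events. If each of the k has the event, the shortfall is (x + k)/(N + k) − x/N. This is largest when x = 0, where it equals k/(N + k).

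- Smallest pool, N = 129 (no placebo participant enters open label): 1/130 = 0.77, 2/131 = 1.53 and 3/132 = 2.27 points.
- Largest pool, N = 194 − k (every other placebo participant enters): 1/194 = 0.52, 2/194 = 1.03 and 3/194 = 1.55 points.

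These are ceilings. If the k people have no event, the pooled proportion is slightly overstated instead, and only exposure is understated.

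**The case against.** **The sentence may be a deliberate refinement.** Table 3 speaks of exposure within the safety population, that row sends the reader to the as-treated rule below, and the exclusion sentence cites Table 3 in turn. One could read it as Table 3 passed through the as-treated label. But Table 3 counts doses taken, names the double-blind period and mentions no exception, and the start-of-data rules in SAP 3.1 and Tables 7 and 9 agree with it. If an exception is meant, it is not stated where the population is defined.

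**The affected group is tiny and its events are still shown.** This stands. Anyone who goes on to open label or LTE is in the population, and SAP 3.6 lists the adverse events separately. That listing does not restore the person to the cumulative tables or to exposure.

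**Stronger readings that the documents do not support:**

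- A reader might infer that the SAP hides harm by charging on-drug events to placebo in the double-blind tables, where one event is 1/65 = 1.5 points. Keeping a mixed-exposure participant in the randomized group is a common as-treated convention. Protocol 10.3.1 has no rule for someone who received both treatments, Protocol Section 10 lets the SAP supersede its methods, and the events are listed separately. There is tension with the protocol's principle, but no contradiction within the SAP.
- A reader might take each error to mean a full bottle: 70 tablets at 2 a day, or 35 days. Clinic visits are 28 days apart and Protocol 6.4.1 has all supplies returned at each, so about 28 × 2 = 56 tablets is the expected ceiling, apart from visit-window days.
- A reader might infer that the rare risks of special interest are the main casualty. Table 7 shows no cumulative column entry for adverse events of special interest or for infections of Grade 2 or higher, and Table 8 does not list uveitis. The loss runs through the general event, serious event, death and liver outputs.

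**Conclusion.** The inconsistency is real and confined to pattern (b). For such a participant the text below Table 3 produces an incomplete exposed population, and Table 3, the start-of-data rules and the protocol's principle all point to inclusion. The practical effect is probably very small and may be nil, because it needs a dosing error while blinded, at least one correct placebo dose, and no later open-label or LTE treatment. The sizes above rest on an assumed one to three adults and on planned arm sizes. The finding does not extend to the double-blind safety comparison or to any efficacy result. It merits correction because it settles who counts as exposed and the change is a matter of wording.

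**What to change.** Either delete the exclusion sentence below SAP Table 3, or add the double-blind period to its exposure condition so that it matches the table. Pattern (b) then enters the population and the other three patterns do not change. The treatment-emergent period should start at the first rilzabrutinib dose actually taken, as SAP 3.1 already provides. If the sponsor does intend an exception, Table 3 should state it and give the reason.

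Leave the as-treated grouping rule for the double-blind tables alone. Moving everyone with any rilzabrutinib dose into the active column, without limiting this to double-blind doses, would also move the planned open-label crossovers and spoil the comparison. Even if limited, it would charge a mis-dosed participant's placebo time to rilzabrutinib.

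The cost is one phrase in the SAP and the matching population flag. ITT efficacy, alpha and power are unaffected.
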